- 5) All subjects must use an emollient twice daily (or more, as needed) for at least 14 days before randomisation and must continue this treatment throughout the trial (including safety follow-up).
- 6) For the first 3 IMP dosing visits (visits 3 to 5) and after re-randomisation (visits 11 to 13), subjects will be monitored after IMP administration for immediate drug reactions for a minimum of 30 minutes with vital signs taken at 30 minutes or until stable, whichever is later (see Section 9.1.3.1).
- 7) eDiary includes: Eczema-related Sleep NRS, Worst Daily Pruritus NRS, Average Daily Pruritus NRS, Patient Days of Topical Treatment Use, PGI-B, and PGI-S; subjects will complete daily from Week -2 to 32, except for Patient Days of Topical Treatment Use which will be completed daily from Week 0 to 32.
- 8) IgE not assessed at screening.

Abbreviations: BSA, body surface area; C-SSRS, Columbia-Suicide Severity Rating Scale; DLQI, Dermatology Life Quality Index; EASI, Eczema Area and Severity Index; EASI75, at least 75% reduction in EASI score; ECG, electrocardiogram; eDiary, electronic diary; EQ-5D-5L, EuroQoL 5 Dimension Health Questionnaire 5 Level; HADS, Hospital Anxiety and Depression Scale; IGA, Investigator's Global Assessment; IgE, immunoglobulin E; IMP, investigational medicinal product; NA, not applicable; NIMP, non-investigational medicinal product; NRS, numeric rating scale; PGI-B, Patient Global Impression of Bother; PGI-S, Patient Global Impression of Severity; POEM, Patient Oriented Eczema Measure; SCORAD, Scoring Atopic Dermatitis; TCS, topical corticosteroid.

Trial ID: LP0162-1339	Date: 29-Aug-2018	Version: 4.0
		Page 25 of 129

Panel 3 Schedule of trial procedures: follow-up including early termination

	SFU ¹ (end of trial)	Nominal Week 16 visit ² (if applicable)	Early termination ³	Unscheduled visit ⁴ (if	Details
Visit	20	11x	(if applicable)	applicable)	(protocol section)
Week	46	16			
Visit window (days)	±3	±3			
Trial products					
Concomitant medication/procedures	X	X	X	X^4	9.4, 9.5
IMP administration, compliance					
TCS (NIMP) dispensing				X ⁴	9.1.2, 9.1.3.2
TCS (NIMP) return			X	X ⁴	9.8.3.2, 9.8.5
Investigators global assessment of	efficacy				
IGA, EASI		X	X	X ⁴	10.3.1.1, 10.3.1.2
SCORAD		X	X	X ⁴	10.3.1.3
Atopic dermatitis flares			X	X ⁴	10.3.1.4
Subjects assessment of efficacy					
eDiary ⁵ completion		X	X	X ⁴	10.3.2
POEM		X	X	X ⁴	10.3.2.7
DLQI		X	X	X ⁴	10.3.2.8
EQ-5D-5L, HADS			X	X ⁴	10.3.2.9, 10.3.2.10
Safety assessments					

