Vital signs	X		X	X ⁴	10.4.1
Physical examination	X		X	X ⁴	10.4.2
EGGs	X		X	X ⁴	10.4.3
Urine pregnancy test	X		X	X ⁴	10.4.4
Serum chemistry, haematology, IgE	X		X	X ⁴	10.4.5
Urinalysis	X		X	X^4	10.4.5
Pharmacokinetics	X		X	X^4	10.4.6
Anti-drug antibodies	X		X	X ⁴	10.4.7
Adverse events	X	X	X	X ⁴	11, Appendix 1, Appendix 2

- Subjects will have a final safety follow-up visit 16 weeks after the last dose of IMP (which is also considered end of trial visit), except subjects who enter the long-term extension trial (conducted under a separate protocol [LP0162-1337, ECZTEND]) for whom the end of trial visit will be the last visit in the present trial before transfer to ECZTEND.
- 2) Subjects who permanently discontinue IMP prior to Week 16 will also attend the nominal Week 16 visit (visit 11x).
- 3) Assessments and procedures performed at Week 16 (see Panel 2) are also to be done at an early termination visit.
- 4) Assessments and procedures to be performed at an unscheduled visit are left at the investigator's discretion; except if due to atopic dermatitis flares, then as a minimum IGA, EASI, concomitant medications/procedures, and AEs are to be assessed.
- 5) eDiary includes: Eczema-related Sleep NRS, Worst Daily Pruritus NRS, Average Daily Pruritus NRS, Days of Topical Treatment Use, Patient Global Impression of Bother, and Patient Global Impression of Severity; subjects will complete daily (Week -2 to 32). Subjects who permanently discontinue IMP prior to Week 16 will complete the eDiary daily until the Nominal Week 16 visit.

Abbreviations: DLQI, Dermatology Life Quality Index; EASI, Eczema Area and Severity Index; ECG, electrocardiogram; eDiary, electronic diary; EQ-5D 5L, EuroQoL 5-Dimension Health Questionnaire 5 Level; HADS, Hospital Anxiety and

Trial ID: LP0162-1339	Date: 29-Aug-2018	Version: 4.0
		Page 26 of 129

Depression Scale; IGA, Investigator's Global Assessment; IgE, immunoglobulin E; IMP, investigational medicinal product; NIMP, non-investigational medicinal product; NRS, numeric rating scale; POEM, Patient Oriented Eczema Measure; SCORAD, Scoring Atopic Dermatitis; SFU, safety follow-up; TCS, topical corticosteroid.

5 Introduction and rationale

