The initial treatment period (randomisation until Week 16) will be analysed separately from the continuation treatment period (Week 16 until Week 32). All objectives and corresponding endpoints are listed in Panel 4.

Panel 4 Objectives and endpoints

Objectives	Endpoints	
Primary objective	Primary endpoints	
To demonstrate that tralokinumab in combination with TCS is superior to placebo in combination with TCS in treating moderate-to-severe AD.	 IGA score of 0 (clear) or 1 (almost clear) at Week 16. EASI75 at Week 16. 	
Secondary objective	Secondary endpoints	
To evaluate the efficacy of tralokinumab in combination with TCS on severity and extent of AD, itch, and health related quality of life compared with placebo in combination with TCS.	 Severity and extent of AD Change in SCORAD from baseline to Week 16. Itch Reduction of Worst Daily Pruritus NRS (weekly average) of at least 4 from baseline to Week 16. Health-related quality of life Change in DLQI score from baseline to Week 16. 	
Additional secondary objectives	Additional secondary endpoints	
To assess the safety of tralokinumab in combination with TCS when used to treat moderate-to-severe AD for 32 weeks.	 AE/SAE frequency by preferred term. Frequency of anti-drug antibodies. 	
To evaluate the efficacy of tralokinumab in combination with TCS on health care resource utilisation compared with placebo in combination with TCS.	 Amount of TCS used through Week 16 (assessed as the amount of TCS weighted from previous visits). Number of AD flares through Week 16. Number of days without topical treatment use from baseline to Week 16 (according to Patient Days of Topical Treatment Use). 	
To support the primary and secondary objectives in the trial.	 Supporting primary endpoints EASI50 at Week 16. EASI90 at Week 16. Change from baseline to Week 16 in EASI score. Supporting severity and extent of AD SCORAD75 at Week 16. SCORAD50 at Week 16. 	

Trial ID: LP0162-1339	Date: 29-Aug-2018	Version: 4.0
		Page 33 of 129

Panel 4 Objectives and endpoints (continued)

Objectives	Endpoints	
Additional secondary objectives	Additional secondary endpoints	
To support the primary and secondary objectives in the trial (continued).	 Supporting itch Change from baseline to Week 16 in Worst Daily Pruritus NRS (weekly average). Supporting health-related quality of life Reduction from baseline to Week 16 of DLQI of ≥4 points among subjects with baseline DLQI ≥4. 	
Maintenance objective	Maintenance endpoints	

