8.5 Discontinuation

A subject may withdraw from trial or from treatment at any time (prior to first dose or during the treatment period) at his/her own request. A subject may be withdrawn at any time at the discretion of the investigator. Discontinued subjects will not be replaced.

Medical reasons for permanent discontinuation of IMP are given in Section 9.7.1.

Trial ID: LP0162-1339	Date: 29-Aug-2018	Version: 4.0
		Page 45 of 129

Subjects who permanently discontinue IMP for any reason will be asked to attend an early termination visit and return to the trial site for 1 or 2 additional visits as indicated below depending on the time of discontinuation of IMP (see the schedule of procedures [Panel 3] for data to be collected at these visits). The investigator will review any AEs which will be followed-up according to Section 11.6, if the subject agrees.

Subjects who permanently discontinue IMP prior to Week 16 will be asked to attend:

- Early termination visit.
- Nominal Week 16 visit (16 weeks after randomisation).
- Safety follow-up visit (16 weeks after last administration of IMP).

Subjects who permanently discontinue IMP at Week 16 or after Week 16 will be asked to attend:

- Early termination visit.
- Safety follow-up visit (16 weeks after last administration of IMP).

If a subject withdraws from the trial, he/she may request destruction of any samples taken and not tested, and the investigator must document this in the site's trial records.

Reason(s) for discontinuation from IMP and withdrawal from the trial must be recorded in the medical records and the eCRF (lack of efficacy, AE, withdrawal by subject, lost to follow-up, death, other). For subjects randomised to IMP but not attending any post-baseline visits, it will be recorded whether any safety evaluations were performed after exposure to IMP.

Lost to follow-up

A subject will be considered lost to follow-up if they repeatedly fail to return for scheduled visits and if the trial site is not able to get in contact with the subject.

Trial ID: LP0162-1339	Date: 29-Aug-2018	Version: 4.0
		Page 46 of 129

The following actions must be taken if a subject fails to return to the trial site for a required visit:

- The trial site must attempt to contact the subject and reschedule the missed visit as soon as possible and counsel the subject on the importance of maintaining the assigned visit schedule and ascertain whether the subject wishes to and/or should continue in the trial.

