10.3.1.4 Atopic dermatitis flares

An AD flare is defined as an acute, clinically significant worsening of signs and symptoms of AD requiring therapeutic intervention (29). For the purpose of this protocol, AD flares are defined as worsening of the disease that requires escalation/intensification of AD treatment reported after initiation of IMP; this will also include initiation or intensification of the TCS (NIMP) supplied to the subjects. Flares will be assessed at the clinic according to the schedule of procedures (see Section 4). Subjects who experience disease worsening between scheduled trial visits should return to the clinic for an unscheduled visit for assessment of flare before initiating the treatment escalation; subjects who return to the clinic for assessment of flares at an unscheduled visit should undergo IGA and EASI assessments, and information on concomitant medications/procedures and AEs should be collected.

Details on rescue treatments and prohibited concomitant medications and procedures for treatment of AD are provided in Sections 9.6 and 9.5.

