12.3.7 Analysis of additional secondary endpoints

Initial treatment period

The analysis of the below additional secondary endpoints will be based on the primary analyses of the primary estimand as specified above for the relevant primary dichotomous endpoints and continuous secondary endpoints, respectively.

The following dichotomous additional secondary endpoints will be analysed according to the primary analysis of the primary estimand for the primary endpoints:

- EASI50 at Week 16.
- EASI90 at Week 16.
- SCORAD50 at Week 16.
- SCORAD75 at Week 16.
- Reduction from baseline (Y/N) of DLQI of ≥4 points (in subjects with baseline DLQI ≥4) at Week 16.

The change from baseline to Week 16 in EASI score and the change from baseline to Week 16 in Worst Daily Pruritus NRS weekly average will be analysed according to the primary analysis of the primary estimand for the continuous secondary endpoints.

To evaluate the efficacy related to health care resource utilisation, the amount of TCS used (assessed as the amount of TCS used between visits), and the number of days without topical treatment use (collected as Patient Days of Topical Treatment Use in the eDiary) will be determined by 2-week periods. The amount of TCS used and the number of days without topical treatment use will each be analysed by a repeated measurements model with an unstructured covariance matrix and the mean modelled as follows:

 $Y = treatment \times visit + region + baseline IGA$

Results obtained after initiation of rescue treatment will be excluded from the analyses.

AD flares will be summarised descriptively as the proportion of subjects having had AD flares at Week 16, the number of AD flares from baseline to Week 16, and the rate of AD flares from baseline to Week 16. The rate of AD flares will be defined as the number of AD flares divided by time at risk, where the time at risk for each subject is the time from treatment start to last visit attended up to Week 16.

Trial ID: LP0162-1339	Date: 29-Aug-2018	Version: 4.0
		Page 97 of 129

Continuation treatment period

To support the maintenance objective of the trial, IGA of 0/1 at Week 32 among subjects with IGA of 0/1 at Week 16 and EASI75 at Week 32 among subjects with EASI75 at Week 16, both after initial randomisation to tralokinumab, will be summarised descriptively by treatment group of the continuation treatment period.

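### Time at risk for the AD flare rate runs to the nominal Week 16 visit after early IMP discontinuation, but no flare assessment is scheduled at that visit

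*Protocol*

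**What the plan says.** Panel 4 (Section 6) lists "Number of AD flares through Week 16" as an additional secondary endpoint. Section 12.3.7 gives three summaries of flares: a proportion, a number and a rate. It states that "AD flares will be summarised descriptively as the proportion of subjects having had AD flares at Week 16", so no test is attached. The rate divides the flare count by person-time, which is fixed as follows: "where the time at risk for each subject is the time from treatment start to last visit attended up to Week 16".

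Under Section 8.5 and footnote 2 of Panel 3, a subject who permanently stops IMP before Week 16 is asked to attend an early termination visit, then visit 11x at 16 weeks after randomisation, then the safety follow-up visit.

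Section 10.3.1.4 has flares assessed at the clinic according to the schedule in Section 4, and adds that "Subjects who experience disease worsening between scheduled trial visits should return to the clinic for an unscheduled visit for assessment of flare". Panel 2 marks flares at all eight visits from Week 2 to Week 16. Panel 3 marks them at early termination and at unscheduled visits only.

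**The concern.** A rate is interpretable when events are looked for throughout the time that enters its denominator. For subjects who stop IMP early and return at 11x, the definition of time at risk reaches Week 16, while the last scheduled flare assessment is at early termination. The gap adds person-time fully but adds flares only as far as subjects come in for unscheduled visits.

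The rate then tends to be too low for these subjects. If early discontinuation differs between arms, the arm with more of it gets the larger understatement and the comparison of rates shifts. The affected summary belongs to a listed additional secondary endpoint, but it lies outside the test hierarchy.

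**Working it through.** **Reading the schedule**

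- In Panel 3 the IGA/EASI and SCORAD rows carry three marks: 11x, early termination and unscheduled. The flare row carries two, under early termination and unscheduled. The 11x cell is blank.
- Footnote 3 of Panel 3 extends the Week 16 assessments to the early termination visit. It does not extend them to 11x.
- Section 8.5 lists no scheduled visit between early termination and 11x.
- Section 12.3.7 neither stops time at risk at early termination nor restricts it to visits with a flare assessment.

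For one subject who returns at 11x, the part of the 16-week denominator without a scheduled flare assessment is:

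- early termination at Week 4: (16 − 4)/16 = 75%
- early termination at Week 8: (16 − 8)/16 = 50%
- early termination at Week 12: (16 − 12)/16 = 25%

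**Size at arm level**

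The protocol states no figure to reproduce here and gives none of the inputs. All of the following are assumptions:

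- d: share of the arm stopping IMP before Week 16
- w: week of early termination
- a: share of those subjects who attend 11x (for the rest, time at risk ends at w)
- c: share of gap flares captured at unscheduled visits
- the true flare rate is the same before and after stopping

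Reported rate as a fraction of the true rate:

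`factor = [(1−d)·16 + d·w + d·a·c·(16−w)] / [(1−d)·16 + d·w + d·a·(16−w)]`

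Worked case with w = 6, a = 0.7, c = 0:

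- Placebo, d = 0.15: (13.6 + 0.9)/(13.6 + 0.9 + 1.05) = 14.50/15.55 = 0.932
- Tralokinumab, d = 0.06: (15.04 + 0.36)/(15.04 + 0.36 + 0.42) = 15.40/15.82 = 0.973
- Tralokinumab/placebo rate ratio multiplied by 0.973/0.932 = 1.044

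| d placebo / tralokinumab | w | a | c | Placebo factor | Tralokinumab factor | Ratio multiplied by |
|---|---|---|---|---|---|---|
| 15% / 6% | 6 | 0.7 | 0 | 0.932 | 0.973 | 1.044 |
| 15% / 6% | 6 | 0.7 | 0.5 | 0.966 | 0.987 | 1.021 |
| 15% / 6% | 6 | 0.7 | 1 | 1.000 | 1.000 | 1.000 |
| 20% / 8% | 4 | 0.9 | 0 | 0.863 | 0.946 | 1.096 |
| 20% / 8% | 4 | 0.9 | 0.5 | 0.931 | 0.973 | 1.044 |
| 10% / 10% | 6 | 0.7 | 0 | 0.955 | 0.955 | 1.000 |
| 5% / 10% | 6 | 0.7 | 0 | 0.978 | 0.955 | 0.977 |
| 5% / 10% | 4 | 0.9 | 0 | 0.966 | 0.932 | 0.965 |
| 20% / 4% | 4 | 0.9 | 0 | 0.863 | 0.973 | 1.127 |

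The last two rows are the extremes over placebo 5–20%, tralokinumab 4–10%, stopping at Week 4–10, attendance 50–90% and capture of 0 or 50%.

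**Shortening only the denominator**

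If time at risk ended at early termination but later flares were still counted, the factor would be `[(1−d)·16 + d·w + d·a·c·(16−w)] / [(1−d)·16 + d·w]`. With w = 6, a = 0.7, c = 0.5:

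- Placebo: (14.50 + 0.525)/14.50 = 1.036
- Tralokinumab: (15.40 + 0.21)/15.40 = 1.014

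The rate would then be overstated by 3.6% and 1.4%.

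**The case against.** **This is a detail for the SAP.** Rules for person-time are often settled there, and Section 12.3.12 foresees an SAP update before the code is broken. But the protocol itself fixes both the denominator and the schedule, and the two do not fit together. An SAP could redefine time at risk. It could not recover flare assessments that were never scheduled.

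**Gap flares are partly captured elsewhere.** A flare is worsening that requires more AD treatment. Medication is recorded with reason and dates, clinically significant worsening is an AE, and both are collected at 11x. Much of the raw information therefore exists, and this part of the objection stands as a reason to expect a small effect. However, Section 10.3.1.4 makes a flare a clinic assessment, and nothing in the protocol derives flares from medication or AE records.

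**The larger shifts are unlikely.** The +13% extreme needs 0.20 × 0.90 × 123 ≈ 22 discontinued placebo subjects to return at 11x with no gap flare captured. Sections 12.3.5.3 and 12.3.6.2 expect few discontinued subjects with Week 16 data. The constant flare rate is also unsupported. This stands: the range shows sensitivity and is no forecast, and even the direction between arms is unknown.

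**The number and proportion of flares are affected too.** Missed gap flares lower all three summaries. That is correct, and it favours collecting the data over only redefining the denominator.

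**Conclusion.** The mismatch is real. As written, time at risk for subjects who stop IMP early and return at 11x includes weeks without a scheduled flare assessment, so their flare rate tends to be understated.

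The effect is probably small: a shift of +2% to +4% in the rate ratio in the central assumed case, none when discontinuation and its timing are equal between arms or all gap flares are captured, and −4% to +13% across the assumed grid. A positive shift makes tralokinumab look less favourable relative to placebo on flare rate. No p-value, alpha allocation or confirmatory conclusion is involved. This is an inexpensive correction worth making, and nothing in the main analysis depends on it.

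**What to change.** Make Panel 3 and Section 12.3.7 agree in one of two ways.

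1. **Add the AD flare item to visit 11x, covering the period since the previous visit.** This keeps the endpoint running through Week 16 and also serves the number and proportion of flares. It costs one item at an existing visit where concomitant medication and AEs are already recorded. The limit is recall: the item would cover up to 12 weeks for a subject who stopped at Week 4, against 2-week intervals for subjects on schedule. It helps only for 11x visits not yet held.
2. **End both the flare count and the time at risk at the last visit with a scheduled flare assessment**, which is early termination for discontinued subjects. This costs one sentence in Section 12.3.7. For these subjects the summary then no longer runs through Week 16, and that should be stated.

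The denominator should not be shortened alone, since flares recorded at later unscheduled visits would then inflate the rate.

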12.3.8 Analysis of other endpoints

12.3.8.1 Efficacy related other endpoints

To further pursue the objectives supported by the five Week 16 endpoints in the confirmatory test hierarchy, the same endpoints will be evaluated at each scheduled assessment up to Week 14, including also the weekly average of Worst Daily Pruritus NRS:

- IGA 0/1 at each scheduled assessment until Week 14.
- EASI75 at each scheduled assessment until Week 14.
- Change in SCORAD from baseline to each scheduled assessment until Week 14.
- Change from baseline to each scheduled assessment through Week 4 to 14 in Worst Daily Pruritus NRS (weekly average).
- Reduction of Worst Daily Pruritus NRS (weekly average) of at least 4 from baseline to each scheduled assessment through Week 4 to 14.
- Change in DLQI score from baseline to each scheduled assessment until Week 14.

Nominal p-values for test of a treatment difference and 95% CI for the difference will be presented at each scheduled visit using the same approach as applied for the primary analysis of the relevant endpoint in the primary estimand.

For the binary endpoints, the same Cochran-Mantel-Haenszel test as for the Week 16 assessment will be applied. For the continuous endpoints, the repeated measurements model already described previously for the Week 16 assessments facilitates that the p-values, treatment differences and 95% CIs can be derived for each visit up to Week 14 in the same analysis that already will be made for the corresponding Week 16 assessments.

Trial ID: LP0162-1339	Date: 29-Aug-2018	Version: 4.0
		Page 98 of 129

12.3.8.2 Patient-reported outcomes

The PROs POEM, DLQI, EQ-5D-5L, and HADS will be summarised by treatment group and visit using descriptive statistics. The summaries will be made separately for initial treatment and continuation treatment. Data from the initial treatment period will be presented for the full analysis set and data from the continuation treatment period will be presented for the continuation treatment analysis set.

The PROs collected daily in the eDiaries (Worst Daily Pruritus NRS, Average Daily Pruritus NRS, Eczema-related Sleep NRS, PGI-B, and PGI-S) will all be summarised over time by treatment group using descriptive statistics. The summaries will be separate for initial treatment and continuation treatment. Data from the initial treatment period will be presented for the full analysis set and data from the continuation treatment period will be presented for the continuation treatment analysis set.

The Average Daily Pruritus NRS collected over the last week prior to baseline (Day -6 to 0) will be used to calculate the baseline average daily itch. A minimum of 4 Average Daily Pruritus NRS scores out of the 7 days is required to calculate the baseline average score.

To investigate a possible early onset of itch relief, a reduction in Worst Daily Pruritus NRS weekly average of at least 4 from baseline to Week 2 as well as a reduction of at least 3 from baseline to Week 2 will be summarised by treatment group. Furthermore, to investigate itch relief during initial treatment a reduction in Worst Daily Pruritus NRS weekly average of at least 3 from baseline to Week 16 will be summarised. These three endpoints will each be analysed according to the primary analysis of the primary estimand for the dichotomous primary endpoints.

In the subgroup of subjects with either HADS anxiety or HADS depression subscale score ≥8 at baseline, the proportion of subjects with both HADS anxiety and HADS depression subscale score <8 at Week 16 will be summarised by treatment group and analysed as described for the primary analysis of the primary estimand for the primary endpoints.

In the subgroup of subjects with a baseline POEM score \geq 4, the proportion of subjects with a reduction in POEM score \geq 4 at Week 16 will be summarised by treatment group and analysed as described for the primary analysis of the primary estimand for the primary endpoints.

The change from baseline to Week 2 in Worst Daily Pruritus NRS weekly average, and the change from baseline to Week 16 in Eczema-related Sleep NRS weekly average, HADS, POEM, and the EQ-5D-5L index will be summarised by treatment group and domain, where

Trial ID: LP0162-1339	Date: 29-Aug-2018	Version: 4.0
		Page 99 of 129

applicable, and analysed according to the primary analysis of the primary estimand for the continuous secondary endpoints. For the Eczema-related Sleep NRS score, the mean over the last 7 days prior to randomisation (Day -6 to 0) will be used as the baseline value.

For the PGI-B, a day of 'no or slight bother' is defined as answering the question with "not at all" or "slightly". The subjects' number of days of 'no or slight bother' will be tabulated per treatment group for the initial treatment period. The mean number of days will be presented with 95% CIs and compared between the 2 treatment groups using an analysis of variance model including treatment, region, and baseline IGA as factors.

